## 5. Specific Aims

The goal of the proposed research project is to explore the acceptability and efficacy of a combined transcutaneous vagus nerve simulation (tVNS) and mindfulness intervention in enhancing sleep and well-being among college students and compare it to mindfulness-only and control conditions with the hypothesis that the combined intervention will have greater efficacy due to synergistic brain effects of tVNS and mindfulness. In addition to experimental results, the proposed project will

generate effect size data to inform future trials of the combined approach and assess the feasibility and acceptability of our study design.

**Specific Aim 1:** To evaluate the feasibility and acceptability of sustained engagement with the Brightmind mindfulness app among college students.

Research question 1.1: Do students find this app acceptable and engage with it consistently across a 4-week period?

Research question 1.2: What are the barriers and facilitators to sustained engagement with the app?

Hypothesis 1.3: Participants who spend more time engaging with the app will see greater improvements in mental health (e.g., stress, anxiety, depressive symptoms, positive affect) and HRV compared to participants who spend less time engaging with the app.

**Specific Aim 2:** To obtain preliminary effect size data on the efficacy of the Brightmind mindfulness app in improving proximal and distal mental health outcomes among college students

Hypothesis 2.1: Participants in the mindfulness-only group will demonstrate greater improvements in mental health (e.g., stress, anxiety, depressive symptoms, positive affect) than participants in the control group

Hypothesis 2.2: Overnight heart rate variability (HRV), positive affect, and interoceptive awareness will be greater in the mindfulness-only group compared to the control group.

Hypothesis 2.3: HRV will increase from before to after each mindfulness session.

**Specific Aim 3:** Determine feasibility and acceptability of the combined tVNS + mindfulness intervention.

Research question 3.1: Do students find this combined intervention acceptable and demonstrate adequate adherence (i.e. use tVNS or sham + mindfulness for at least 10 minutes/day at least 4 days/week for 2 weeks)?

Research question 3.2: What are the barriers and facilitators to adherence with the combined intervention?

Hypothesis 3.3: The combined intervention will be well-tolerated and receive positive acceptability ratings.

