## 6. Research Plan

**6.1 Study timetable and logistics.** The study will consist of an intake-training session and a 4-week intervention phase. Participants will complete brief weekly online surveys during the intervention phase and a follow-up online survey 4-weeks after the end of the intervention period. Face-to-face interaction with subjects will take place at the University of Florida McKnight Brain Institute (MBI) during the intake-training visit, the return of study equipment, and the distribution of participant payment

**Figure 1** Visualization of the study protocol and timeline.

**6.2 Experimental design.** As participants are scheduled for intake visits, they will be assigned to either a tVNS group (tVNS + mindfulness or sham + mindfulness) or a non-tVNS group (mindfulness only or control) by the research coordinator based on practical considerations (i.e. tVNS device availability) to expedite study completion. Within each of these groups, participants will be randomized via alternating order to either the active or control condition (in other words, once a participant is assigned to a tVNS group, they will then be randomized to either the tVNS + mindfulness or sham + mindfulness group). This process will repeat until each group has the target number of participants.

In the initial visit, a research assistant will review the appropriate informed consent form. During this process, participants assigned to a stimulation group (tVNS + mindfulness or sham + mindfulness) will be told that they have been randomized to receive one of two different types of noninvasive vagal nerve stimulation, that we think one of the conditions may be more effective, and that they have a 50/50 chance of being in that group. For participants randomized to the non-stimulation groups (mindfulness only or control), they will be told that they have been randomly assigned to use one of two mobile app interventions, that we think one of the interventions may be more effective, and that they have a 50/50 chance of being in that group. After providing written informed consent, participants will complete a brief health questionnaire as part of our inclusion/exclusion screening (see section 6.5). If participants screen out after signing the informed consent, the session will end, and any data collected will be kept in a locked filing cabinet.

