**Stimulation Device:** We will use the Soterix Medical RELIfit-Tragus transcutaneous electrical nerve stimulation devices. For details, see “Device type” in my.irb. Stimulus pulses will be alternating in polarity to reduce tissue irritation and will be delivered at 20Hz, 200  $\mu$ s pulse width, within the range of published stimulus parameters.

**Calibration:** Participants will undergo calibration during the intake-training visit. Prior to calibration, participants will be informed that the stimulation intensity will be slowly increased until they report any discomfort and then reduced to a comfortable level for the remainder of the study. Individual sensitivity to tVNS stimulation will then be evaluated with a structured stepped-ramp protocol, with a brief pause at each step during which the participant will be asked what the stimulus felt like to them and if they experienced any discomfort. The stimulation intensity will then be set to 80% of the discomfort threshold for the active tVNS group and near to 0% (just enough to keep device on) of the discomfort threshold for the sham stimulation group. If the participant reports irritation with stimulation during this ramp up procedure (which can last ~15 minutes), electrode adhesion will be checked (if there is poor contact, it can affect the sensation) and stimulation intensity will be reduced if necessary (any change will be documented). If the participant further indicates discomfort, stimulation will be discontinued. If the patient evidence dizziness/lightheadedness or if a comfortable level of stimulation is not achievable at calibration, the participant will be removed from the study (this will be documented).

**Blinding:** Participants will be blinded to condition and told that, after calibration, the stimulus intensity will be set to below the calibration (discomfort threshold) level and that they may not feel the stimulation once reduced. We have used this form of psychological sham approach in

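### Calibration can remove participants after active or sham has been assigned, and no rule counts those removals in the tolerability result

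*Combined protocol and SAP*

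**What the plan says.** Section 6.2 (Experimental design) places participants in the stimulation or non-stimulation pair when the intake visit is scheduled. Within a pair, "participants will be randomized via alternating order to either the active or control condition". The sequence is described as "once a participant is assigned to a tVNS group, they will then be randomized to either" active or sham. At consent, participants in the stimulation pair "will be told that they have been randomized to receive one of two different types of noninvasive vagal nerve stimulation". On recruitment, the section adds: "This process will repeat until each group has the target number of participants". Table 1 gives 20 per group and Section 6.3 gives 80 in total.

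The Calibration paragraph (Section 6.6, Nerve Stimulation) states: "Participants will undergo calibration during the intake-training visit". One stepped ramp to the discomfort threshold is described for everyone in the stimulation pair. Intensity is then "set to 80% of the discomfort threshold for the active tVNS group and near to 0% (just enough to keep device on") in the sham group. A participant who shows dizziness or lightheadedness leaves the study, and likewise "if a comfortable level of stimulation is not achievable at calibration, the participant will be removed from the study". Each removal is to be documented. The Blinding paragraph states only that participants are blinded.

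Hypothesis 3.3 in Section 5 reads: "The combined intervention will be well-tolerated and receive positive acceptability ratings". In Section 6.6, the acceptability, appropriateness, feasibility and usability scales are given only at week 4. The Analysis Plan compares tolerance and acceptability between groups by ANOVA and dropout by group with a chi-square test.

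**The concern.** An exclusion that follows assignment is a problem if it can depend on the arm, because active versus sham is the contrast that isolates stimulation. It is also a problem for Aim 3, whichever arm is affected. A person removed because stimulation could not be made comfortable is direct evidence about tolerability. If that person is missing from the tolerability data and the place is filled by someone else, Hypothesis 3.3 is judged mainly on people who have already passed a tolerance filter. The mindfulness-only and control groups face no such filter.

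**Working it through.** **1. Order of events.** Section 6.2 gives consent, then health screening, then the baseline survey, then equipment training. Calibration takes place at the same intake visit. The moment at which active or sham is set is not stated. The consent wording speaks of randomization as already done, which places it before calibration. Removal at calibration is therefore removal after assignment.

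**2. Does removal depend on the arm?** There are two readings.

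- *Comfort judged on the ramp.* The ramp is the same in both arms, the irritation step is tied to it, and the dizziness criterion names no arm. Expected losses are then equal.
- *Comfort judged at the assigned intensity.* Participants are told beforehand that intensity will be raised to discomfort and then lowered to a comfortable level that is kept for the study. The removal rule uses the same notion of a comfortable level. The level kept is 80% of threshold in active and near 0% in sham, and near 0% would almost always be comfortable. Nothing says that the staff judging comfort are unaware of the arm.

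The text does not settle which reading is meant.

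**3. How are removals counted?** Those removed leave the study, so they give no week-4 scores. The Analysis Plan defines no analysis population and does not mention calibration removals. Section 6.2 does not say whether a removed participant counts toward the 20.

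**4. Arithmetic.** The plan's only sample-size figure reproduces: 4 × 20 = 80. It gives no removal rate, so the rates below are assumptions. Let *p* be the proportion of those starting calibration who are removed. Suppose that removals are replaced and are the only intolerance.

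- Number starting per arm to retain 20 = 20/(1 − p). At p = 0.05 this is 20/0.95 = 21.1. At p = 0.10 it is 20/0.90 = 22.2.
- Tolerability among those retained is 100%. Among all who started it is 1 − p, which is 95% or 90%.
- Chance of at least one removal among 20 who start = 1 − (1 − p)^20, which is 0.64 at 5% and 0.88 at 10%.
- If removal arises only on the common ramp, a 5% rate gives 21.1 starting in active and 21.1 in sham, so no imbalance is expected. If it arises only in active, the numbers starting are 21.1 versus 20.0 at 5%, and 22.2 versus 20.0 at 10%.

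**5. Would the dropout test reveal an imbalance?** Suppose calibration removals were counted as dropouts and occurred only in active. Exact binomial enumeration was used, with a two-sided level of 0.05 (an assumption) and group sizes rounded to 21 versus 20 and 22 versus 20. The uncorrected chi-square test has power of about 2% at a 5% removal rate and 17% at 10%. Fisher's exact test has about 0.3% and 6%.

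**The case against.** The strongest reply is that nothing in the calibration rule names an arm. The ramp and the dizziness criterion are common. An intensity of 80% of a person's own threshold lies below that threshold by construction, and the paragraph allows intensity to be reduced if necessary. A reader might infer that the rule removes more active than sham participants and so biases the efficacy contrast. The documents do not establish that. It holds only if comfort is judged at the assigned intensity, which is plausible but unstated.

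Two further replies also have force. Filling to target describes assignment, so replacement of removed participants is an inference. Removals are documented, and nothing bars them from the attrition figures or the dropout test, so it would be too strong to say that the plan excludes them from the tolerability result.

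These replies leave the core standing. Removal follows assignment on the consent wording, the week-4 scales cannot include those removed, and no rule says how to count them. Counting them in the dropout test would not be enough, because that test has little power at these sizes.

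The filter also separates the stimulation pair from the other two groups, which bears on the comparisons with control in Hypotheses 4.1 and 4.2. That adds little here, because the pairs are formed on practical grounds and not by randomization, which is a larger and separate matter.

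**Conclusion.** The point holds as a post-assignment exclusion with no counting rule. Whether it differs between active and sham is open: it can if comfort is judged at the assigned intensity, and in expectation it does not if comfort is judged on the ramp. Under either reading, tolerability is judged mainly on people who passed a tolerance filter.

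The size is illustrative. At an assumed removal rate of 5% to 10%, a figure of 100% among those retained would be 90% to 95% among all who started calibration, an overstatement of 5 to 10 percentage points. A reader might take the 18% skin-irritation figure in Section 7.1 as a bound on removals. It is a side-effect rate across other studies and not a rate of failing calibration, so it does not serve. I give no figure for bias in the sleep or mood outcomes. That would need a removal rate by arm and a link between intolerance and outcome, and the documents give neither.

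**What to change.** Leave the sponsor's removal and stopping criteria as they are, and change the order and the reporting.

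- Set active or sham only after calibration has been completed and passed, and issue the device codes then. The codes carry the group's intensity, which is derived from the calibrated threshold, so they depend on calibration in any case.
- Keep the staff who calibrate unaware of the next assignment. Under simple alternation, anyone who knows the last assignment knows the next, so someone not involved in calibration must hold the sequence.
- State at what point in calibration comfort is judged, so that it is done in the same way for everyone before assignment.
- Change the consent wording from already randomized to will be randomized.
- Use everyone who started calibration as the denominator for stimulation feasibility and tolerability, and count calibration removals as not tolerating. Report this for the stimulation pair as a whole, because those removed would then belong to no arm.
- State that the 20 per group are counted from assignment after calibration.

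Removal then cannot depend on the arm under either reading, so the ambiguity no longer threatens active versus sham. The filter absent from the non-stimulation groups remains but is disclosed. The cost is protocol and consent wording, a reordered intake visit, and a possibly slightly less favourable tolerability figure.

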## 7. Possible Discomforts and Risk

**7.1 Transcutaneous Vagal Nerve Stimulator.** Previous studies using some form of stimulation found that some side effects may occur including itching, redness, discomfort, and tingling/mild pain at the stimulation site. These side effects usually end shortly after stopping stimulation. If the electrodes are not well placed then participants might experience mild pain, although the researchers will adjust the electrode placement if this happens. Researchers will also explain how to adjust electrodes for when the subjects are at home. Other less common potential side effects (observed in <1% of study populations) include nausea, headache, heart palpitations, dizziness, vocal hoarseness, and nasopharyngitis. It is important to note that these less common side effects were primarily found in studies of clinical populations with a variety of stimulation methods (e.g., cervical stimulation, bilateral stimulation, longer lengths of stimulation) that are not being used in this study. Thus, while these side effects have been observed in some prior studies, we do not anticipate that are likely to occur in this study of healthy college students.

We will be using a Soterix Medical taVNS device. Their website describes the device safety thusly:

*“taVNS on the other hand, delivers electrical stimulation to the auricular branch of the vagus nerve (ABVN), an easily accessible target that innervates the human ear (Peukar*

*and Filler 2002). Over the last decade, several groups have demonstrated the safety and tolerability of this method, including central and peripheral nervous system effects, and behavioral effects in neuropsychiatric populations (Kreuzer et al 2012, Clancy et al 2014, Rong et al 2016, Bauer et al 2016). taVNS is also being explored in individuals to enhance cognitive and social functioning (Jacobs et al 2015, Jongkees et al 2018, Colzato et al 2018). Furthermore, side-effects of taVNS are minimal, with skin irritation or redness being the most common side-effect. In a review of 51 studies with 1322 human participants receiving tVNS, the most common side effect was local skin irritation (%18). Authors conclude tVNS is well tolerated and safe (Redgrave et al., 2018).”*

- Peuker, E.T., & Filler, T.J. The nerve supply of the human auricle. *Clinical Anatomy*. 15 (1), 35-37 (2002).

**7.3 Mood Assessments:** Questions about mood and personality can sometimes be uncomfortable (e.g., talking about things that make you sad or anxious). If participants experience distress while completing these questionnaires, they will be instructed to contact a research assistant who will be able to provide community mental health resources.

**7.4 Wearable Sensors:** The wrist monitor is comparable to wearing a standard wristwatch. If the band is too tight, there is a risk of skin irritation. Similar risks apply to the chest band. Both bands are adjustable to ensure participant comfort.

**7.5 Breach of Confidentiality.** Breach of confidentiality is highly unlikely because all information will be identified with a participant code and stored in a locked file cabinet. Only study staff will have access to this database. All staff are or will be fully trained in relevant ethical principles and procedures, including confidentiality.

Once a participant completes the entirety of the study (i.e. returns the equipment and/or receives payment) and the payment is updated according to UF's Human Participant Payments guidelines, the subject's contact information and student identification/social-security-number will be redacted from the questionnaires and payment receipts.

**7.6 Data and Safety Monitoring Plan.** The investigative team will meet regularly to discuss data and safety monitoring issues. Any issues identified during the course of these meetings will be handled in a manner consistent with the University of Florida's policies.

## **8. Possible Benefits**

A potential benefit of participating in this study is experiencing a short-term improvement in mood and sleep quality. No direct long-term benefits can be reasonably expected from this study, except if the mindfulness training app intervention shows preliminary efficacy and participants continue using it on their own after the study is over. The information garnered from this study may provide valuable data on the optimization of the tVNS technology, which has the potential to be a cheap, effective, and safe tool for augmenting effects of mindfulness practice.

## **9. Conflict of Interest**

There are no known conflicts of interest.

## **10. Participant Payment**

Participants will be compensated for their time and effort participating in the study. The amount is specified on my.irb.ufl.edu and the consent form.

